## DEFINITIONS

**Day 1:** The first day a subject receives plasma exchange for treatment of TTP.

**Treatment Response:** 2 consecutive days with platelet count  $\geq 150,000/\mu\text{L}$

**Durable Treatment Response:** Treatment Response that persists for  $\geq 30$  days after discontinuation of plasma exchange.

**Exacerbation:** Recurring TTP  $\leq 30$  days after a Treatment Response and discontinuation of plasma exchange.

[figure not shown]
**Refractory TTP:** Failure to achieve a Treatment Response by day 28, or failure to achieve a Durable Treatment Response by day 60.

**Composite Primary Endpoint:** Exacerbation or Refractory TTP.

**Relapse:** Recurring TTP  $> 30$  days after Treatment Response.

**Observation Period:** The interval of 2 years after a subject first achieves a Durable Treatment Response.

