### 1.2 Secondary Endpoints

#### 1.2.1 Clinical and Safety Endpoints

- Incidence of Durable Treatment Response
- Number of days to Durable Treatment Response
- Number of plasma exchanges to Durable Treatment Response
- Incidence of relapse
- Numbers of days to relapse
- 4 week, 1 year and 2 year incidence of death
- Incidence, type and severity of treatment-related adverse events

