## 2. BACKGROUND AND SIGNIFICANCE

### 2.1. Utility of ADAMTS13 data in TTP

The introduction of plasmapheresis with plasma exchange has increased survival in patients with TTP from less than 10 percent to 80 percent and is the only therapy demonstrated to be effective in a randomized clinical trial (Rock 1991). Plasma exchange rapidly restores circulating levels of the von Willebrand factor cleaving protease, ADAMTS13, and removes inhibitors to the enzyme. Although clearly beneficial, plasma exchange does not correct the primary cause of the disorder. More than 30% of patients with TTP have at least one relapse within 2 years (Kremer 2008). In addition plasma exchange may itself cause significant morbidity. One study documents a 31% risk for major complications, including a 3% fatality rate (McMinn 2003).

An autoimmune etiology of acquired TTP in adults is strongly supported by the finding of circulating ADAMTS13 inhibitors due to IgG autoantibodies. These inhibitors are found in 48 to 80% of individuals with idiopathic TTP (Moake 2002, Tsai 2003, Veyradier 2001). ADAMTS13, a von Willebrand factor-cleaving protease, regulates the size of von Willebrand factor (VWF) multimers. Deficiency of ADAMTS13 activity is associated with persistence of ultra large molecular weight VWF (ULVWF) multimers. ULVWF avidly binds to platelets, leading to

microvascular platelet deposition, the hallmark of TTP. Subsequent series identified severe ADAMTS13 activity deficiency in 30% to 80% of cases of TTP (Lammle 2005).

Although severe deficiency of ADAMTS13 activity (<5%) appears to be specific for TTP, the syndrome can also be seen in subjects with less severe deficiency and even normal levels of ADAMTS13 making diagnostic decisions difficult (George 2004). However, the risk of relapse is higher (~45%) for patients with persistent severe ADAMTS13 deficiency during remission, and essentially all of these patients have severe ADAMTS13 deficiency when they relapse (Zheng 2004). ADAMTS 13 inhibitors also correlate with relapses, delayed response to plasma exchange, refractory disease, and early death (Zheng 2004, Bohm 2005, Coppo 2006, Kremer Hovinga 2010).

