## 9. STATISTICAL CONSIDERATIONS

### 9.1 Sample Size and Power

Review of 40 patients with TTP at BJH who would have met the inclusion criteria indicates that the composite primary endpoint rate was 55% in this historical group. Assuming a 10 percent of composite primary endpoint rate in the treated group and 40 historical controls, 14 treated patients are needed to have a 90% power to detect a 45 % difference in the incidence of exacerbation at the 5% significance level. We will enroll 20 patients total and expect to enroll 12 patients per year. Therefore, recruitment may be complete within less than 2 years. The time would be reduced by participation of other regional hospitals.

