### 9.2 Data analysis

Fisher Exact tests will be used to compare the incidence of the composite primary endpoint, Durable Treatment Response, Relapse, treatment-related adverse events and 4-week, 1-year and 2-year incidence of death between the treated group and historical controls. We will consider Chi-Square test to examine differences in the type and severity of adverse events between the treated group and historical controls.

The time to Durable Treatment Response and Relapse will be described by Kaplan-Meier estimators and log rank tests. The effects of patient characteristics will be evaluated with Cox proportional hazards models. Numbers of plasma exchanges to Durable Treatment Response will be compared with non-parametric tests (e.g. Kruskal-Wallis analysis of variance).

The value of ADAMTS13 biomarker data for predicting Exacerbation, Durable Treatment Response or Relapse will be analyzed by logistic regression. The relationship between ADAMTS13 biomarker parameters and platelet count, LDH or B cell levels will be investigated with linear regression models.

Rituximab levels and the extent of B cell depletion will be analyzed as stratified categorical data with Cochran-Mantel-Haenszel statistics.

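### The plan gives no rule for deaths in the Kaplan-Meier and log-rank analysis of time to Durable Treatment Response; default censoring would overstate the probability of response.

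*Combined protocol and SAP*

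**What the plan says.** Section 1.2.1 lists "Number of days to Durable Treatment Response" as a secondary endpoint, and separately "4 week, 1 year and 2 year incidence of death". Section 9.2 gives the method for the first: "The time to Durable Treatment Response and Relapse will be described by Kaplan-Meier estimators and log rank tests". It names no censoring rule and no competing-risk method. Incidence of death and incidence of Durable Treatment Response are also compared as proportions, by Fisher's exact test.

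The Definitions section makes Durable Treatment Response a "Treatment Response that persists for" at least 30 days after plasma exchange stops, and sets Day 1 at the first plasma exchange. It counts a patient without Durable Treatment Response by day 60 as Refractory TTP, which is part of the composite primary endpoint; section 5.2.5 repeats this. Section 8.2 lists death as an off-study criterion, together with loss to follow-up and entry into another investigational trial.

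For the comparison group, section 9.1 cites a "Review of 40 patients with TTP at BJH who would have met the inclusion criteria" and reports that "the composite primary endpoint rate was 55% in this historical group". It does not say how many of the 40 died. On the treated side, "We will enroll 20 patients total".

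**The concern.** A patient who dies before Durable Treatment Response can never reach it. Censoring that patient at death lets the Kaplan-Meier estimator assume a later chance of response equal to that of the survivors still under observation. The curve then estimates response in a setting without death, yet it will be read as the proportion of patients who respond by a given day.

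Three things are at stake:
- The response curve is too high in any group with early deaths, and the excess grows with their number.
- A log-rank test with these deaths censored compares the rate of response among those still alive. It does not compare the probability of response and does not register a difference that arises through early death.
- The same death would be handled in two opposite ways: read literally, as a failure in the composite at day 60, but as censored and still able to respond in the secondary analysis.

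Speed of response is part of the rationale in section 2.4, so this curve will be looked at. Time to Relapse has the same gap, because a patient who dies in remission cannot relapse.

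**Working it through.** **The plan's own figure.** The plan gives no figure for the time-to-response analysis. Its one calculated figure is 14 treated patients against 40 controls (55% versus 10%, 90% power, 5% level). A two-sided pooled normal approximation reproduces it: 14 is the smallest number reaching 90%, with power 90.7%. It concerns the composite and does not depend on what follows.

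**Step 1: timing.** Day 1 is the first exchange, and durability needs at least 30 days after the last one. The earliest possible date is therefore about 1 + 30 = day 31. A 4-week death occurs by day 28, so every such death precludes the endpoint.

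**Step 2: how many deaths.** The documents do not report deaths among the controls. Section 2.1 says that plasma exchange "increased survival in patients with TTP from less than 10 percent to 80 percent". Applied to 40 controls, that gives 40 × (1 − 0.80) = 8 deaths (binomial 95% range 3 to 13). This is a background figure for TTP in general with no time horizon, and only deaths before response matter here. I therefore treat 8 as one scenario and also use 2 and 4. The composite rate does not settle the matter: 40 × 0.55 = 22 failures is compatible with 8 early deaths and equally with none.

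**Step 3: size of the overstatement.** Let N = 40, D = deaths before any response, F = survivors who never respond, and R = N − D − F responders. With no other censoring:
- 1-KM with deaths censored = R / (N − D)
- true cumulative incidence = R / N

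| D | F = 0 | F = 4 | F = 8 |
|---|---|---|---|
| 0 | 100% vs 100% | 36/40 = 90% vs 90% | 32/40 = 80% vs 80% |
| 2 | 38/38 = 100% vs 95% | 34/38 = 89% vs 85% | 30/38 = 79% vs 75% |
| 4 | 36/36 = 100% vs 90% | 32/36 = 89% vs 80% | 28/36 = 78% vs 70% |
| 8 | 32/32 = 100% vs 80% | 28/32 = 88% vs 70% | 24/32 = 75% vs 60% |

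Each cell gives 1-KM, then the true proportion. The gap is about 4 to 5 points with 2 deaths, 8 to 10 with 4, and 15 to 20 with 8. Spreading the deaths over days 1 to 60, with responses on days 35 to 90, changes these values by less than one point.

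**Step 4: the log-rank test.** Simulation of 40 controls and 20 treated patients, with equal speed of response among survivors. Assumptions: deaths uniform over days 1 to 30; response at day 30 plus a lognormal time (median 12 days, log-SD 0.5); window to day 60; at least 2,000 trials per setting; two-sided 5% level.

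| Mortality, control / treated | Rejection, deaths censored | Rejection, deaths kept as non-responders |
|---|---|---|
| 20% / 0% | about 5% | about 43% |
| 20% / 5% | about 6% | about 25% |
| 20% / 10% | about 6% | about 14% |
| 10% / 0% | about 5% | about 16% |
| 10% / 5% | about 6% | about 8% |
| 20% / 20% | about 6% | about 6% |

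Repeat runs agree within about three points (41% to 44% for the first row). None of these mortality pairs is an assumption of the plan.

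**The case against.** The case on the other side is substantial.

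- **The plan never says that deaths are censored.** This stands. The off-study list does not say how death enters the analysis, and Kaplan-Meier and log-rank could be run with deaths held as non-responders to the end of the window. The defect is a missing rule whose default is unfavourable.
- **A reader might infer that the documents imply about 8 deaths among the controls.** They do not. The 80% is a general literature figure. The controls were selected for severe ADAMTS13 deficiency, with sepsis, cancer, transplant and other conditions excluded. Section 2.1 also links inhibitors to early death, so even the direction of any difference from 80% is unknown.
- **A reader might infer that the log-rank test is invalid, or that it would miss a benefit the trial expects.** With deaths censored it is a valid test of the cause-specific hazard of response, and rejection near 5% is the correct size when speed among survivors is equal. The plan posits no mortality difference; its hypothesis is about exacerbation and refractory disease.
- **Other analyses cover part of the gap.** Fisher's tests on death and on incidence of Durable Treatment Response can count deaths properly. For 8/40 versus 0/20 deaths, the two-sided Fisher p is about 0.043.

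These points limit the finding, but none repairs the response curve. If deaths are censored, 1-KM is too high whatever the Fisher tests show.

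**Conclusion.** The concern holds as an unspecified rule on a secondary endpoint, where the default reading gives a biased curve and disagrees with the plan's own Refractory TTP definition. A cheap and better method exists.

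The size depends on the number of deaths before response, which the documents do not give. If all survivors respond, 1-KM reads 100% against a true 95%, 90% or 80% for 2, 4 or 8 such deaths in 40. The last case needs the background 80% survival figure to apply to these controls and every death to come early. With no such deaths there is no bias. The effect on the test is large only when mortality differs clearly between groups, small at 10% versus 5%, and immaterial at equal mortality.

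For Relapse the gap is the same in kind, but no figure in the documents allows its size to be estimated. The primary analysis and the sample size are unaffected.

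**What to change.** Add to section 9.2:
- **Time to Durable Treatment Response:** estimate cumulative incidence with death as a competing event and compare groups by Gray's test. With complete follow-up to a fixed window, keeping patients who die in the risk set as non-responders to the end of that window is equivalent. State the window.
- **Time to Relapse:** estimate cumulative incidence with death as a competing event.
- **Reporting:** give the number of deaths before Durable Treatment Response in the treated group and among the 40 controls.
- **If the log-rank test is kept:** label it a comparison of cause-specific hazards, not of response probability.

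The cost is a few sentences in the SAP and a count of control deaths from records already reviewed; the sample size does not change. The downside is that response curves will look slightly lower, and the test will reflect speed of response and early death together, so the results should be read beside the separate death comparison.

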## ABSTRACT

The ART study (Adjuvant Rituximab in TTP) is a pilot safety/efficacy study of adjuvant low dose rituximab (100 mg/week x 4 doses) plus standard plasma exchange and corticosteroids for the treatment of thrombotic thrombocytopenic purpura (TTP) with severe ADAMTS13 deficiency. Results for study subjects will be compared to historical controls treated initially with plasma exchange and corticosteroids. This study proposes to test the hypothesis that adjuvant low dose rituximab may decrease the incidence of composite primary endpoint (exacerbations or refractory disease) in acquired TTP with severe ADAMTS13 deficiency. A novel ADAMTS13 assay will be used to identify patients with TTP and severe ADAMTS13 deficiency for enrollment, and to assess the utility of ADAMTS13 as a biomarker for response to therapy and prognosis.

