### 1.1 Primary Endpoint

- Incidence of composite primary endpoint, Exacerbation or Refractory TTP

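### Logistic regression on ADAMTS13 markers would rest on about 2 events: not estimable in roughly 15–23% of trials at a 10% event rate, and extremely imprecise in the rest

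*Combined protocol and SAP*

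**What the plan says.** On the biomarker analysis, section 9.2 has one sentence for the clinical outcomes: "The value of ADAMTS13 biomarker data for predicting Exacerbation, Durable Treatment Response or Relapse will be analyzed by logistic regression". It does not name the ADAMTS13 measure, the sampling time, the patients included, the method of estimation, or what happens if events are too few for a fit.

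The size of the data comes from section 9.1: "We will enroll 20 patients total", and "Assuming a 10 percent of composite primary endpoint rate in the treated group and 40 historical controls, 14 treated patients are needed". That 10% is for the composite, which section 1.1 gives as "Incidence of composite primary endpoint, Exacerbation or Refractory TTP". Section 9 assumes no relapse rate. The background (section 2) cites relapse of 10% in a study of full-dose adjuvant rituximab, 14% (10 of 69) in a review of rituximab in TTP, and more than 30% within 2 years in TTP generally.

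Biomarker utility is a declared purpose. The Abstract says the assay will be used "to assess the utility of ADAMTS13 as a biomarker for response to therapy and prognosis", and section 1.2.2 lists the matching laboratory objectives under the secondary endpoints.

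**The concern.** Logistic regression draws its information from the rarer outcome category. By the plan's own figures that category holds about two patients. With no event there is nothing to fit. If the marker values of the few events all lie beyond those of the other patients (complete separation), the likelihood has no finite maximum. Short of that, estimates swing widely and Wald standard errors are unreliable.

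All three outcomes in the sentence are affected. Exacerbation is one part of the 10% composite. Under the Definitions, a patient without a Durable Treatment Response by day 60 counts as Refractory TTP, so non-response by day 60 also falls inside that 10%. Relapse is rare if the cited rituximab rates apply.

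At stake is whether a stated aim yields a usable result, and whether the analyst must choose a fallback after seeing that the model has failed.

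**Working it through.** **Reproducing the plan's figure.** Inputs from section 9.1: 55% in 40 controls, 10% in the treated group, 5% level (taken as two-sided), 90% power. Pooled z test with 14 treated:
- Pooled rate: (22 + 1.4)/54 = 0.433.
- Null SE: √[0.433 × 0.567 × (1/40 + 1/14)] = 0.154.
- Alternative SE: √[0.55 × 0.45/40 + 0.10 × 0.90/14] = 0.112.
- Power: Φ[(0.45 − 1.96 × 0.154)/0.112] = Φ(1.32) = 0.907. With 13 treated it is 0.888, so 14 reproduces.

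**Expected events among 20 treated.**
- Composite: 20 × 0.10 = 2.0. Exacerbation alone: at most 2.0.
- Non-response by day 60: at most 2.0.
- Relapse: 20 × 0.10 = 2.0 to 20 × 0.14 = 2.8; or 1.8 to 2.5 among 20 − 2 = 18 durable responders. At 30%, about 5 to 6.

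**Chance of very few events** (binomial, n = 20, 10%): P(0) = 0.9²⁰ = 0.122; P(1) = 0.270; P(2) = 0.285; P(3 or fewer) = 0.87.

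**Behaviour of the model.** The documents give no marker effect, so it is assumed: one standard-normal marker with a true odds ratio (OR) of 1, 2 or 3 per SD. Simulated trials had n = 20 and a 10% event rate. Not estimable means no event or complete separation. Maximum-likelihood (ML) columns describe fitted trials; Firth columns describe all trials with at least one event.

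| True OR | Not estimable | ML median OR | ML geometric mean | ML 5th–95th percentile | Firth median | Firth 5th–95th percentile |
|---|---|---|---|---|---|---|
| 1 | 15% | 0.99 | 1.01 | 0.16–6.05 | 1.01 | 0.27–3.7 |
| 2 | 18% | 2.06 | 2.7 | 0.45–33 | 1.80 | 0.60–9.1 |
| 3 | 22% | 3.21 | 5.0 | 0.71–98 | 2.50 | 0.81–14.6 |

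Separate simulations put the not-estimable share at up to 23%. At a true OR of 3 the 90th percentile of the fitted ML estimates is about 27. About 30% of fitted estimates are more than twice the truth and 20% are below half of it. The root mean square error of the log odds ratio is 1.3–1.9 for ML and 0.8–1.0 for Firth.

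**Sensitivity of the not-estimable share** (true OR 1 to 3):
- Exacerbation alone at 5%, n = 20: 41–48%.
- Relapse, n = 18: 20–27% at a 10% rate, 9–16% at 14%, 0.4–2% at 30%.
- Marker split 50/50 into high and low, 10% rate, n = 20: 58–66%.

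**Tests.** At n = 20 and 10%, the Wald test rejects in 0.2% of trials at a true OR of 1 and in 1–3% at 2 to 3. The likelihood-ratio test from the same model rejects in 31% at a true OR of 3, but also in 7.8% at 1. The rank-sum test rejects in 17% at 3. Its exact two-sided p-value cannot fall below 2/20 = 0.10 with one event, or below 2/190 = 0.011 with two (190 = 20 × 19/2).

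**The case against.** The strongest reply has four parts.

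First, a reader might infer that every odds ratio the model returns will be inflated. The numbers do not support that. The median fitted value is within about 7% of the truth, there is no inflation when the marker has no effect, and about one estimate in five is below half the true value. The excess is in the geometric mean and the upper tail.

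Second, a reader might infer that logistic regression as such has no power here. Near-zero power belongs to the Wald test, which section 9.2 does not name. A likelihood-ratio test does far better, though it rejects somewhat too often under no effect.

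Third, neither maximum likelihood nor a treated-only analysis is written down. Section 9.1 says the 40 controls would have met the inclusion criteria, which include ADAMTS13 activity below 10%, so they may have a baseline value. Pooling gives 22 + 2 = 24 composite events in 60 patients and no failures. That is fair, but the sentence lists Exacerbation, Durable Treatment Response and Relapse rather than the composite. Serial ADAMTS13 sampling (sections 6.1.4 to 6.1.8, Tables 3 to 5) is scheduled only for study subjects, and the eligibility limit narrows the one activity value that both groups would share. Treated-only is the more natural reading; that it has to be inferred is itself a gap.

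Fourth, no method makes two events informative, and Firth pulls the typical estimate down (median 2.50 for a true 3). That stands. Firth's advantage is a finite estimate whenever at least one event occurs, and a much shorter tail.

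**Conclusion.** The concern holds as one of failed fits and extreme imprecision, not of systematic inflation. With about 2 expected events, a 10% rate, a treated-only analysis and an assumed odds ratio of 1 to 3 per SD, maximum-likelihood logistic regression is not estimable in about 15–23% of trials. The remaining estimates are centred about right but very widely spread, with a long right tail, and a Wald test on them is nearly inert.

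A reader might take a failure rate of one trial in five as a property of the plan. It is not: it depends on an event rate that section 9 does not give for these individual outcomes, and on a marker effect that the documents do not give at all. The 12% from zero events needs only the 10% rate. The total runs from about 1% (relapse at 30%) to above 40% (Exacerbation at 5%).

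The consequence is limited to a secondary laboratory objective in a pilot study. The primary Fisher comparison, the sample size and the safety analyses are untouched.

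**What to change.** Replace the sentence in section 9.2 with one that:
- names the ADAMTS13 measure, the sampling time and the analysis set (treated patients) for each outcome;
- uses Firth-penalised or exact logistic regression, one marker at a time, with profile-penalised-likelihood or exact intervals and no Wald tests;
- adds a rank-sum comparison and an area under the ROC curve with an exact interval, for patients with and without the event;
- reports marker values descriptively if no event occurs;
- labels the results as estimation only.

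The cost is wording, with no new data or patients. Intervals will stay wide, and Firth shrinks the typical estimate somewhat. In return the error of the log odds ratio falls from 1.3–1.9 to 0.8–1.0, a cut of roughly 40–50%, and the fallback is fixed before the data are seen.

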months). Of eight patients with available ADAMTS13 data after rituximab treatment, seven had recovery of normal ADAMTS13 activity and disappearance of a detectable inhibitor (Ling 2009).

A prospective study in France (Froissart 2012) compared 22 adults with refractory TTP treated with rituximab and plasma exchange to 53 historical controls who received plasma exchange with or without vincristine. The time to a durable remission was significantly shorter for patients receiving rituximab ( $P = 0.03$ ), although the plasma volume required to achieve a durable remission was not significantly different compared to controls. Of the rituximab-treated patients, none relapsed within the first year although three relapsed up to 3 years later. Treatment with rituximab produced a rapid and profound depletion of peripheral B-cells that lasted 9 months and correlated with a higher level of ADAMTS13 activity and lower antibody titers. These differences were no longer significant after 12 months. No severe side effects occurred.

Thus, treatment with rituximab normalizes ADAMTS13 and induces durable remissions in >90% of patients with refractory or relapsing TTP. Late relapses have occurred in ~10% of these patients after 9 months to 4 years; all but one had a prolonged remission when retreated with rituximab (Sadler 2008). These results suggest that adjuvant rituximab might increase the rate of remission and reduce relapses for patients with severe ADAMTS13 deficiency at diagnosis. In fact, a recent study of adjuvant full dose rituximab (375 mg/m^2 weekly x 4) observed a 10% relapse rate compared to 57% in historical controls (Scully 2011).

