## **2.4. Proposed Study of Low-Dose Adjuvant Rituximab for TTP**

The substitution of low dose for standard dose rituximab would reduce the drug cost 7-fold to approximately \$2,000 for a 4 week course, which approximates the cost of one plasma exchange procedure. Low dose rituximab (100 mg) may also have a decreased risk of complications. Two studies of low dose rituximab for ITP reported mainly mild infusional reactions. The rate of serious complications is probably low but not known precisely: one of 59 patients with ITP treated with low dose rituximab developed interstitial pneumonia that responded to steroids (Provan 2007, Zaja 2010).

Based on the currently available data we propose a pilot study to determine whether adjuvant low dose rituximab, in addition to standard therapy with plasma exchange and corticosteroids, can shorten the time to treatment response and reduce the risk of exacerbation for patients with TTP caused by ADAMTS 13 deficiency.

We will use a novel assay to evaluate the utility of ADAMTS 13 as a biomarker to assess the response to therapy and predict the risk of relapse. If successful this therapy would not only improve patient outcomes but also would be cost saving compared to standard dose, salvage rituximab, which is the current standard of care.

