**Table 4: Schedule of Measurements After Plasma Exchange (PE) is Stopped for Treatment Response**

	First 30 days of no PE	Months 1 to 3	4 Months to 2 years
Assessment			
Clinical status	1 per week $\pm$ 2 days	1 per month $\pm$ 7 days	Every 3 months for 2 years $\pm$ 14 days
Medication log	1 per week $\pm$ 2 days	1 per month $\pm$ 7 days	Every 3 months for 2 years $\pm$ 14 days
Laboratory			
Surveillance Panel	1 per week $\pm$ 2 days	1 per month $\pm$ 7 days	Every 3 months for 1 year after first PE $\pm$ 14 days
Chemistry Panel	1 per week $\pm$ 2 days	1 per month $\pm$ 7 days	1 year after first PE $\pm$ 14 days
ADAMTS13 activity and antibody	Day 7 $\pm$ 2 days and day 30 $\pm$ 7 days	1 at month 3 $\pm$ 14 days	Every 3 months for 2 years after first PE $\pm$ 14 days
Peripheral smear	Day 7 $\pm$ 2 days		
Serum IgG, IgM and IgA			One year after first PE $\pm$ 14 days

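### The logistic regression of Relapse on ADAMTS13 has no stated way to use relapse times, incomplete follow-up or the quarterly ADAMTS13 series

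*Combined protocol and SAP*

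**What the plan says.** Section 9.2 gives one sentence to the biomarker analysis of clinical outcomes: "The value of ADAMTS13 biomarker data for predicting Exacerbation, Durable Treatment Response or Relapse will be analyzed by logistic regression". It does not name the ADAMTS13 measurement or its time point, and it gives no rule for repeated values or for patients whose follow-up is incomplete.

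The same section does plan survival methods for Relapse: "The time to Durable Treatment Response and Relapse will be described by Kaplan-Meier estimators and log rank tests" and "The effects of patient characteristics will be evaluated with Cox proportional hazards models". ADAMTS13 is not mentioned in either sentence.

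The rest of the protocol treats Relapse as timed and ADAMTS13 as serial:

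- Section 1.2.1 lists "Numbers of days to relapse" as a secondary endpoint, and the Definitions set a 2-year observation period from the first Durable Treatment Response.
- Section 6.1.5 schedules ADAMTS13 at day 7, day 30 and month 3 after plasma exchange stops, then quarterly to month 24. Table 4 has "Every 3 months for 2 years after first PE".
- Section 2.4 gives one purpose of the assay as to "predict the risk of relapse".
- Section 8.2 ends participation at death, loss to follow-up or entry into another investigational trial.

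**The concern.** The question is whether ADAMTS13 measured during remission warns of a later relapse. An ordinary logistic model needs the series reduced to fixed summaries per patient, and each obvious summary has a problem.

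- **Baseline value.** Eligibility requires activity below 10%, so the range is narrow by design.
- **Early remission value (day 7, day 30, month 3).** Section 2.2 reports that after rituximab, in one prospective study, "none relapsed within the first year although three relapsed up to 3 years later". It also gives late relapses at 9 months to 4 years and, in a literature review, a median time to relapse of 22 months. An early value may be taken well before the risk period.
- **Last or lowest value.** The look-back differs between patients. Without a cut-off, it can include the sample that section 6.1.8 schedules on the first day after relapse is diagnosed. That sample describes the relapse and does not predict it.

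The first choice can hide a useful marker and the last can manufacture one. A patient lost at month 6 and one followed relapse-free to month 24 would also both count as no relapse, unless a rule says otherwise.

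**Working it through.** **1. The plan's own figure.** None is given for this analysis. The only stated sample size, 14 treated patients in section 9.1, concerns the primary composite. It reproduces: 10% versus 55%, 40 controls, two-sided 5% level, pooled normal approximation gives 14 treated patients with 90.7% power. It has no bearing on the ADAMTS13 question.

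**2. Samples available (sections 6.1.3 to 6.1.5).** A relapse-free patient has days 7 and 30 plus months 3, 6, 9, 12, 15, 18, 21 and 24, which is 2 + 8 = 10 post-exchange samples. Seven of the 10 fall at month 6 or later. Adding baseline, and one at days 9–13 if still on exchange, gives 11–12. With 20 patients that is 220–240 samples. If one value per patient were used, 20/240 to 20/220 = 8–9% of them would enter.

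**3. Expected relapses.** Section 2.2 gives relapse rates after rituximab of about 10%, and of 10/69 = 14%. I assume they carry over to this trial and that the analysis rests on the 20 treated patients, since no ADAMTS13 schedule is given for the historical controls.

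- At 10%: 20 × 0.10 = 2.0 expected; P(0 or 1) = 0.9^20 + 20 × 0.1 × 0.9^19 = 0.39.
- At 14%: 20 × 0.14 = 2.8 expected; P(0 or 1) = 0.86^20 + 20 × 0.14 × 0.86^19 = 0.21.

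Some of those relapses came after 2 years, which would lower the count. The review's median follow-up was only about 10 months, which would raise it.

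**4. How much the choice of value can matter.** Simulation with 20 patients, 8 quarterly visits and 2,000 runs per row. Every input is an assumption. A share of patients become severely deficient; some are already deficient at month 3, and the rest become so uniformly over months 9–24. Comparison: Fisher test of month-3 deficiency against relapse yes/no, versus an exact risk-set test on current deficiency at each relapse time (standing in for a time-updated Cox model).

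| Patients becoming deficient | Of these, visible at month 3 | Quarterly relapse risk, deficient / not | Power, month-3 value | Power, current value | Gain (points) |
|---|---|---|---|---|---|
| 20% | 0% | 20% / 0.2% | 0.00 | 0.57 | 57 |
| 30% | 10% | 20% / 0.2% | 0.04 | 0.81 | 77 |
| 40% | 10% | 20% / 0.2% | 0.06 | 0.90 | 84 |
| 30% | 50% | 20% / 0.2% | 0.60 | 0.92 | 32 |
| 20% | 10% | 10% / 1% | 0.02 | 0.26 | 24 |
| 20% | 50% | 10% / 1% | 0.21 | 0.37 | 16 |
| 30% | 90% | 10% / 1% | 0.47 | 0.54 | 7 |
| 30% | 90% | 20% / 0.2% | 0.93 | 0.96 | 3 |

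A second simulation used a month-1 value, dropout of 0.005 per month and monthly relapse hazards of 0.03–0.06 if deficient and 0.003 if not. With 20 patients it gave power of 15–38% for the early value against 39–90% for time-updated status.

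**5. Is the logistic form itself the problem?** With risks of 20% / 0.2%, I also pooled patient-quarters (latest value against relapse in the next quarter) and tested the 2×2 table by Fisher as a proxy for discrete-time logistic regression. Power was 0.72–0.98, against 0.64–0.97 for the risk-set test and 0.00–0.66 for the month-3 value. The proxy ignores calendar quarter, so its small edge means little. The loss comes from a single early value with a yes/no outcome over the whole follow-up, and not from the logistic link.

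**The case against.** The strongest reply is that section 9.2 never commits to one value per patient. Its wording does not exclude a logistic model on patient-quarters, and step 5 shows that such a model recovers essentially all the information. The month-3 comparator in step 4 is my choice and is not in the plan. This stands: a reader might infer that the plan fixes a single ADAMTS13 value, but it is silent. The defect is an unspecified predictor in a model whose ordinary form does not suit the outcome.

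A reader might also infer that relapse times are thrown away. They are not, because Kaplan-Meier, log rank and Cox methods are planned. They are simply not linked to ADAMTS13.

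Nor do the documents describe a late ADAMTS13 fall within patients. Section 2.2 says that the advantage over controls was no longer significant after 12 months, which recovery in the controls would also produce. Section 2.1 says that "the risk of relapse is higher (~45%) for patients with persistent severe ADAMTS13 deficiency during remission", and persistent deficiency is the kind an early sample could detect. A late fall is a reasonable inference and no more.

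Finally, this is a secondary laboratory objective in a 20-patient pilot, and a Cox model with 2 or 3 events is fragile too. That is correct. It argues for an exploratory label and sparse-data methods, but it does not justify leaving the predictor undefined.

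**Conclusion.** The point holds as a mismatch between the named model and the data collected, together with an unspecified predictor. For Relapse, ordinary logistic regression takes no account of event time or incomplete follow-up, and nothing in section 9.2 says how the quarterly series enters or that samples from the relapse itself are kept out. The objection is much weaker for Exacerbation and Durable Treatment Response, which are decided over a short window.

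The size is uncertain. The direction was the same in every scenario, but the gain ran from about 3 to over 80 points. It turns on how much deficiency is already visible early and on how strongly deficiency raises the relapse risk, and the documents give neither. A claim of a guaranteed gain, such as at least 30 points, is not supported: it needs a 100-fold risk contrast (20% against 0.2% per quarter) and no more than half of the deficiency visible at month 3.

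No primary, safety or sample-size conclusion depends on this. It is a cheap improvement to an analysis that serves a stated aim.

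**What to change.** For Relapse, replace the logistic sentence in section 9.2 with a prespecified time-to-event analysis:

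- Cox model with time origin at Durable Treatment Response, and the most recent ADAMTS13 activity and antibody as time-updated covariates. With so few events, fit them in separate models. A discrete-time logistic model on patient-quarters is an acceptable equivalent.
- Censor at death, loss to follow-up or entry into another trial.
- Exclude any sample taken on or after the day relapse is diagnosed.
- Use penalised or exact inference, and label the analysis exploratory because about 2 to 3 relapses are expected.

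Keep logistic regression for Exacerbation and Durable Treatment Response, and state which ADAMTS13 time point is used for each.

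The cost is SAP wording and slightly more programming; every sample is already scheduled. The downside is that values are carried forward for up to about 3 months between visits.
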